Hypothesis 2: The EX intervention will lead to improved secondary outcomes of VIPN (lower P-CIN scores), Neuropathic pain (lower NPS and CTCAE scores), Quality of Life (higher Peds QL V4 scores), and Physical activity (higher total activity time, more time with higher heart rate throughout the day, more exercises completed, and higher oxygen consumption) for patients at the end of the intervention (T2) compared to baseline (T1).

Hypothesis 3: The EX intervention will lead to increases in Biomarkers of NGF, SNAP1, GAP 43, and PDGF-BB and Chemerin at the end of the intervention (T2) compared to baseline (T1).

Hypothesis 4: Changes in key predictor variables (e.g. self-efficacy, outcome expectations, support) will be associated with changes in outcomes (e.g. neuropathy, pain, and quality of life).

C. BACKGROUND & RATIONALE

Vincristine-induced peripheral neuropathy (VIPN)

The most diagnosed pediatric cancer (ages 0-19) is leukemia (26%) with acute lymphoblastic leukemia (ALL) being the most common (75%)⁷, while lymphoblastic lymphoma (LL) is a fast-growing type of Non-Hodgkins Lymphoma (NHL) accounting for 2% of all NHLs¹³. Patients with both ALL and LL receive Vincristine as part of their standard treatment plan utilizing the same treatment and dosing schedule¹³.

Due to improved multidrug treatment regimens over the past 40 years, the 5-year survival rate for these children has increased from 57% to 80% - 90%^{7,14}. However, **due to vincristine exposure, we know that approximately 78% of the children with ALL will develop severe peripheral neuropathy (Vincristine-induced peripheral neuropathy: VIPN)**⁵. To date there is no study on children with LL. VIPN is observed very early in treatment, usually within the first four weeks¹⁵. The development of VIPN is characterized by progressive motor, sensory and autonomic loss of function and usually results in dose reductions of vincristine during treatment and thus an overall loss of therapeutic efficacy¹⁶⁻¹⁸. While we know that methotrexate, another chemotherapeutic agent used in the treatment of ALL, can also have toxic effects, severe neuropathy induced by this drug is very rare (<1%) and manifests as a reversible optic neuropathy not a peripheral neuropathy^{19,20}.

Long-term health outcomes in survivors of childhood cancers

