The Fitbit activity tracker was chosen for this feasibility study due to its versatility and effectiveness within younger populations of children. The FitBit's ease of use, comfort, design and feedback features were important factors for all age groups (children and AYA). Researchers in some studies utilized the Fitbit activity tracker to assess adherence to home-based activity programs⁷⁵.

I. PROCEDURES

[figure not shown]
I.1 Overview

For this feasibility study, 40 pediatric patients with a diagnosis of ALL or LL who have a TNS of ≥ 3 at the end of four weeks of vincristine treatment will be enrolled from Riley Hospital for Children, Indiana University Health North Hospital, . Children and AYA will be recruited during their first four weeks after diagnosis and if they have a TNS ≥ 3 at the time of baseline (week 4-6 T1) they will be enrolled into the study. During T1 patients will complete all questionnaires, neuropathy exams, and provide blood samples and then again at week 14 (T2). Neuropathy exam may be performed during weeks 4 through 6 to accommodate regimented clinical visits. Exercise assessments will be performed on week 7. Subjects will check-in with the exercise therapist during weeks 9, 11, and 13 at a minimum, or once a week during the study if they choose (weeks 7-15). These in-

person sessions will take approximately 15 minutes, and the therapist will provide education, evaluate the subject's exercise plan, review exercises, set goals, and make plans to optimize adherence to the exercise program.

All study visits will take place before or after routine clinic visits so that patients and their families do not have to make additional trips to the four hospital sites. EX sessions will be completed by patients at home using instructional videos that will be given to participants during their study orientation.

I.2 Intervention timeline

I.3 Exercise (EX) Intervention

The EX intervention will include both an in-person exercise schedule and at-home video EX sessions (See Appendix I and II). The EX intervention will be designed and led by an AFAA (Athletics and Fitness Association of America) certified physical fitness trainer with fifteen years' experience and a professional with a PhD in an Exercise Science related field.

In-Person Exercise Sessions:

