Total Neuropathy Score - Pediatric Vincristine (TNS-PV): The TNS-PV is a multidimensional instrument that will be used to measure peripheral neuropathy symptoms and signs in children from 5-25 years old receiving vincristine. Modified from the original Pediatric Total Neuropathy Score (Ped-TNS)⁵, the instrument assesses proximal extension of numbness, tingling, and neuropathic pain, vibration and temperature sensation, strength, tendon reflexes, constipation (autonomic neuropathy), and hoarseness/voice (cranial nerve neuropathy)⁷⁷. A multiplexed measuring system was developed that simultaneously ranks the 8-10 subjective and objective parameters. These parameters provide qualitative information on symptoms, nerve conduction and sensory tests on a scale of 0 for 'none' to 4 for 'severe'. The individual scores are added together to provide a single measure of neuropathy called a Total Neuropathy Score (See Appendix IV).

Total Neuropathy Score – Clinical Evaluation (TNSc): The best acknowledged method to assess the severity and changes in chemotherapy-induced peripheral neurotoxicity is through determination of the Total Neuropathy Score. The TNSc is an instrument that will be used to measure peripheral neuropathy symptoms and signs in young adults from 19-25 years old receiving vincristine. The TNSc (See Appendix V) consists of seven items with scores correlating significantly with the National Cancer Institute-Common Toxicity Criteria v. 2.0 ($p < 0.001$, $r^2 = 0.77$, $r = 0.88$, 95% confidence limits 0.849–0.914). With a test-retest coefficient of 0.86-0.87 (Academy of Oncologic Physical Therapy). The TNSc is more sensitive than the NCI-CTC 2.0 in detecting mild sensory damage because it detected changes in the range of 1–3 points even in 50% of those patients who were scored as unchanged using the NCI-CTC 2.0 score⁷⁸.

Pediatric Chemotherapy-Induced Neuropathy (P-CIN) Survey: the Pediatric Chemotherapy-Induced Neuropathy Survey (P-CIN) is a self-report measure of pain for ages 5-17. The P-CIN is designed to rate symptoms of CIPN (numbness, tingling and pain over the past 2-3 days). The P-CIN consists of 13 items for ages 5-17. Each of the 12 items is rated using the 6-point Faces Pain Scale (See Appendix VIII).

Neuropathic Pain

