Ferrans & Powers Quality of Life Index: Total quality of life will be measured using the Ferrans and Powers Quality of Life Index Version III and is a 66-question index designed to evaluate social, psychological, family, and health satisfaction (See Appendix XI). This assessment is valid for ages 19 and above. Higher scores indicate greater satisfaction in quality of life with an internal Cronbach's alpha of 0.93⁸¹.

Social Learning Theory Questionnaire

Self-Efficacy: There is currently no exercise self-efficacy scale for children and AYA's with cancer. We have adapted the Bartholomew physical activity self-efficacy scale for children and AYA's for use in our study⁸². We have adapted the original self-efficacy scale by adding two questions that are specifically neuropathy related and replaced the term exercise where physical activity had been used. Responses to the questions are limited to Yes/No and not applicable. (See Section 1 Appendix XII).

Support: The support module was taken from a larger validated scale developed by Liang et al (2014) which measures physical activity self-efficacy, enjoyment, and exercise social support for children⁸³. The support section of the questionnaire consists of 10 questions rated on a 5 point scale from None to Very often. The items assess support children and AYA's receive from parents and peers to facilitate exercise. We have adapted the term physical activity to the term exercise for this study (See Section 2 Appendix XII).

Outcome Expectations: We adapted an existing exercise outcomes expectations questionnaire from the adult literature for the purposes of our study. The survey consists of 10 items targeting exercise outcome expectations. Patients are asked to rate each item on a 5 point scale. Items were edited for developmental level/appropriateness⁸⁴. (See Section 3 Appendix XII)

Physiological Parameters

[figure not shown]
Fitbit activity tracker: All patients will be instructed to wear their Fitbit activity trackers every day during waking hours throughout the intervention period. The Fitbit activity tracker (specifically the Charge 2) has a five-day battery life and an “always-on” heart rate tracking system. It is an accelerometer that is worn like a small wristband and records data on movement (steps, HR, distance and activity), total activity minutes, heart rate and total minutes of inactivity including sleep. The data is stored on the device and then can be downloaded wirelessly to a computer⁷⁵.

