Adherence will be measured by self-report of session completion (See Appendix III) and activity tracking via FitBit. All participants will be asked to fill out a short 5 question survey following their EX session regarding their workout, energy level, food intake, and sleep quality. Parents will be asked to initial and review the questions and add any additional comments they feel would be helpful for us to know. The Daily Log is designed not just to aid the child in planning and goal setting, but also to give parents an opportunity to provide positive reinforcement for the child's daily exercise. The patients will also be asked to hit a start EX button on the FitBit at the beginning of the intervention which shows that they have started the video and then hit it again upon completion. The instructor in the video will prompt the child to start and stop their FitBit as a reminder.

Acceptability

Patient Satisfaction Survey: This satisfaction survey was adapted from an existing exercise intervention satisfaction survey⁹⁰. The satisfaction survey consists of 13 items, and they will be asked to respond to each item using a 5 point scale. Patients will provide feedback on the exercise program, exercise videos and therapist support. There is also an open response question for additional feedback (See Appendix XIV).

Parent Satisfaction Survey: Parents will also be asked to complete a satisfaction survey regarding the exercise program, exercise videos, and therapist support. To assess the satisfaction of the parents/caregivers of pediatric cancer patients (peripheral neuropathy symptoms) while participating in an exercise intervention during the Consolidation Phase of chemotherapy⁹⁰. The satisfaction survey consists of 13 items, and they will be asked to respond to each item using a 5 point scale. (See Appendix XV)

Domain, Measurements and Schedule for Study Outcomes

Domain	Measure	# Items	Schedule	
			T1	T2
Predictors				
Demographics	Gender, age, race/ethnicity, pre-diagnosis exercise level		X	
Medical Characteristics	Neuropathy, Weight, ALL/LL diagnosis		X	
Physical Functioning	Baseline Standardized Fitness Assessment	13	X	
Self-efficacy	SLT Exercise Questionnaire	10	X	
Outcome Expectations	SLT Exercise Questionnaire	10	X	X
Support	SLT Exercise Questionnaire	10	X	X
Primary Outcome				
Feasibility	Percentage of subjects that can complete the 8-week intervention FitBit data Daily Log	6	Weeks 6-13	

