Based on our conceptual model, we will also examine associations between change scores for predictors and change scores for primary and secondary outcomes. For example, we will estimate Pearson correlations between changes in self-efficacy, outcome expectations, support, neuropathy, pain, and quality of life.

We will also examine whether or not the circulating protein biomarkers at T1 are associated with VIPN severity at T1 using Spearman correlations and whether initial or dynamic levels of the circulating biomarkers are predictive of intervention efficacy. The associations between VIPN and the genetic and circulating biomarkers will be analyzed through generalized linear mixed models, which includes a random subject effect to account for the correlation of observations from the same subject.

J.3 Missing Data

We expect minimal dropout at 14 weeks (primary endpoint for the proposed trial) and have inflated the sample size to account for the expected 15% attrition, so we anticipate it will not create any substantial bias in the results. To aid in future studies, we will compare baseline characteristics among those who complete the study and those who do not to determine if there are any characteristics associated with study completion.

K. RISKS OF PARTICIPATION AND PROTECTION OF HUMAN SUBJECTS

K.1 Risks

Possible risks to participation in this study are breach of confidentiality, physical distress or emotional distress due to study participation. All contact with the participant will be documented beginning at the consent process through completion of the study. All documentation will be reviewed regularly. Any events that might indicate increased participant physical distress or emotional distress will be promptly brought to the attention of the PI and reported to the IRB and DSMC per reporting guidelines listed below. We will promptly report to the IRB any instances of consent withdrawal due to distress. The IRB will be informed at least annually of our data and safety monitoring, summary of participant status, and any changes in the risk of the study.

Prevention of injuries have been addressed through 1) video design, 2) safety reminders during videos and fitness assessment and 3) muscle soreness. The video design is based on a specific gradual workout design to ensure safety for the most deconditioned patients. The study has incorporated beginner (seated or bed), intermediate (bridge between beginner and advanced) and advanced EX chapters.

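### Two neuropathy items added to the self-efficacy scale may account for part of its planned correlation with neuropathy and pain; report the correlations with and without them.

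*Combined protocol and SAP*

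**What the plan says.** Section I.4 (Social Learning Theory Questionnaire, Self-Efficacy) describes a physical activity self-efficacy scale adapted for this trial: "We have adapted the original self-efficacy scale by adding two questions that are specifically neuropathy related". The schedule table at the end of I.4 gives self-efficacy 10 items. The natural reading is that these include the two added ones, though the table does not say so. The items themselves are in Appendix XII, a separate file.

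Section B, Aim 2 Hypothesis 4, states: "Changes in key predictor variables (e.g. self-efficacy, outcome expectations, support) will be associated with changes in outcomes (e.g. neuropathy, pain, and quality of life". Section J.2 gives the method: "For example, we will estimate Pearson correlations between changes in self-efficacy, outcome expectations, support, neuropathy, pain, and quality of life".

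The primary neuropathy measure, the TNS-PV, is partly symptom report. Section I.4 says that "the instrument assesses proximal extension of numbness, tingling, and neuropathic pain, vibration and temperature sensation, strength, tendon reflexes" are among its components. The P-CIN and the Neuropathic Pain Scale, also in I.4, are self-reports of symptoms or pain.

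The plan nowhere scores the self-efficacy scale without the added items, and it does not analyse those items separately.

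On timing, the schedule table marks self-efficacy at T1 only ("Self-efficacy SLT Exercise Questionnaire 10 X"), while outcome expectations and support are marked at both visits. Section I.1 says otherwise: "During T1 patients will complete all questionnaires, neuropathy exams, and provide blood samples and then again at week 14 (T2".

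**The concern.** Hypothesis 4 is the test of the conceptual model in section E: does exercise self-efficacy change together with neuropathy, pain and quality of life? To answer that, the predictor has to measure something distinct from the outcome. If two of its items respond to the child's neuropathy, the total score will move when neuropathy moves, even when confidence about exercise in general has not changed.

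The likely sign makes this awkward. As neuropathy falls, answers to the two items would tend to become more favourable. The induced correlation is then negative, which is the direction that would be read as support for the Social Learning Theory model. A zero correlation would no longer be the right reference value for self-efficacy being unrelated to neuropathy, and the estimate carried into a later trial would be shifted.

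**Working it through.** **Inputs from the documents.** Section H.1 plans 40 enrolled with 15% attrition, so n = 40 × (1 − .15) = 34 for change scores. It assumes a T1–T2 correlation of .4 for TNS-PV and type I error .05. Section I.4 gives 2 added items, and its schedule table gives 10 in all.

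**The plan's own figure.** H.1 claims 80% power for a .5 SD change by paired t-test. With n = 34 the noncentral t gives 80.8%. For the 2-point change, the SD of the difference is 3.66 × √(2 × (1 − .4)) = 4.01, so d = 2/4.01 = .499 and power is 80.6%. Both reproduce. The plan states no figure for the correlations, so H.1 only fixes n.

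**Assumptions, not in the documents.** Eight items have no relation to neuropathy. The two added items have a loading λ on concurrent neuropathy, varied from .3 to .7. Self-efficacy is independent of neuropathy, with a T1–T2 correlation of .5. Items load on self-efficacy at .5 or .7. The total is a simple sum of yes/no items.

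**Step 1: threshold.** At n = 34 a Pearson correlation reaches two-sided p < .05 when |r| is at least t/√(n − 2 + t²), with t the 97.5% point on 32 df. This gives .339.

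**Step 2: closed form.** Take ten equal-variance change items with inter-item correlation c. Two of them have correlation of size ρ with neuropathy change, and the correlation between those two is the larger of c and ρ². The induced correlation is

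|r| = 2ρ / √(8 + 56c + 2 + 2·max(c, ρ²) + 32c).

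With ρ = .5 and c = .2 the variance is 8 + 11.2 + 2 + .5 + 6.4 = 28.1, so |r| = 1/√28.1 = .19. On the Fisher scale, (atanh .339 − atanh .189) × √31 is about .90, so p < .05 occurs in about 19% of trials. The result depends strongly on the assumptions: ρ = .2 with c = .5 gives |r| = .05 and 6%, while ρ = .7 with c = 0 gives |r| = .42 and 71%.

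**Step 3: simulation with yes/no items, n = 34.**

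| Loading λ of the two items | Mean r, 10 items | p < .05, 10 items | p < .05, 8 items |
|---|---|---|---|
| .3 | about -.08 | 7–8% | 4–5% |
| .5 | about -.13 | 10–13% | 4–5% |
| .7 | -.18 to -.21 | 17–22% | 4–5% |

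Ranges reflect separate runs and the choice of self-efficacy loading, with the weaker loading giving the larger distortion. The 4–5% for the eight-item score follows from the assumption that those items are unrelated to neuropathy. It shows that the two items are the source in this model, not that the shorter score would be clean in practice.

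**Step 4: set against sampling error.** For r = -.13 at n = 34, the Fisher interval is tanh(atanh(-.13) ± 1.96/√31), or about -.45 to .22. The induced shift is smaller than the uncertainty in any single estimate.

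**The case against.** The strongest reply is that the decisive premise cannot be checked. The plan calls the two items neuropathy related and places them in a self-efficacy scale. If they ask whether the child feels able to exercise despite symptoms, they measure condition-specific self-efficacy, and some link with neuropathy belongs to the construct. This stands. A reader might infer that the answers are bound to follow neuropathy, but the documents support only that they may.

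It is also fair to say that J.2 speaks of estimating correlations, with no test, alpha or decision rule, so a rejection rate is an imperfect yardstick. The trial is a feasibility study and Hypothesis 4 is secondary. TNS-PV also covers examined signs such as vibration, strength and reflexes, which limits direct duplication. All of this reduces the weight of the point without removing it: the shift in the estimate remains whether or not a test is done.

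Dropping the two items is not a complete cure. Weakness or pain may lower confidence on any exercise item, and the shorter score loses content that was added because no scale existed for this population. That is a good reason to report both scores and not replace one with the other.

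A reader might also take the response format ("Responses to the questions are limited to Yes/No and not applicable") to mean that children whose symptoms resolve will lose points, which would mask a true association. The documents do not support that. They give no scoring rule and do not say that a not-applicable answer counts as zero. That is a missing detail, not a demonstrated bias.

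**Conclusion.** The point holds in conditional form. The scale contains two neuropathy-related items, its change is to be correlated with change in neuropathy and pain, and the plan has no way to tell shared content from an effect of exercise self-efficacy. If the items respond to symptoms with loadings of .3 to .7, the induced mean correlation is about -.08 to -.21, and p < .05 occurs in about 8 to 22% of trials instead of 5%.

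This rests on the assumed loadings, on the other eight items being unrelated to neuropathy, on the 10 listed items including the two added ones, and on self-efficacy being measured at both visits. The distortion is modest and confined to a secondary hypothesis. It does not affect feasibility, acceptability or the T1–T2 change in TNS-PV. It would be wrong to conclude that any observed correlation is an artefact or that Hypothesis 4 cannot be examined. What is limited is how far a correlation using the full score supports the conceptual model.

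**What to change.** Add to J.2 that correlations of self-efficacy change with neuropathy and pain change will be reported both with and without the two added items, that the two items will also be summarised separately, and that Hypothesis 4 will be called supported for self-efficacy only if the association remains without them. State there in advance what counts as remaining.

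The cost is a sentence or two and no new data. The downside is that the eight-item score is slightly less reliable, which makes a true association somewhat harder to see at n = 34.

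Separately, reconcile the schedule table in I.4 (self-efficacy at T1 only) with section I.1 (all questionnaires at T1 and T2). Without a T2 measurement there is no self-efficacy change score, and this part of Hypothesis 4 cannot be analysed with or without the added items.

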An integral component of wearable activity trackers, such as Fitbit, is the automation of real-time physical exercise tracking and heart rate⁸⁵. The Fitbit activity tracker builds upon pedometer-based activity interventions with a more sophisticated interface using the Internet or a mobile application. This allows for the implementation of behavioral change techniques, tailoring of goals, tracking of progress and documenting adherence to home-based EX protocol with minimal use of resources^{85,86}. There is an exercise study which shows that children wearing Fitbits use them to self-regulate and as a result increase their activity levels as shown by an increase in their overall steps⁶⁴.

Even though the EX sessions are not purely aerobic EX, the Fitbit can detect increases in heart rate during these sessions. Specifically, the EX sessions include aerobic EX, dynamic resistance training, and isometric EXs and thus, will rely on both aerobic and anaerobic energy sources. During aerobic components of the program, the heart must do more work to pump an increased cardiac output to working muscles, and heart rate generally increases in a linear fashion to increases in EX intensity. Heart rate increases during dynamic resistance EX will be due initially to vagal withdrawal and then stimulation of sympathetic nervous system by central command and from muscle chemo and mechanoreceptors. During isometric EX, muscle fibers compress small blood vessels, preventing new oxygen-laden blood from reaching affected muscle tissue. Thus, as long as the muscle contraction is maintained, heart rate will steadily rise. Therefore, detectable elevations in heart rate are expected during EX sessions, albeit through several different mechanisms. Although the immediate effect of isometric exercises is to inhibit blood flow and therefore oxygen to the muscles, the long-term effects are vasodilation, thus an increase in oxygen. In addition, isometric exercises help maintain strength of the muscles and enhance stabilization. These types of exercises are often included in rehabilitation situations and therefore can contribute to improving neuropathy⁸⁷.

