To address Aim 1, adherence in the intervention group will be measured through a 5 question survey at each treatment and also through start/stop on the Fitbit. Adherence scores will be summarized across time with descriptive statistics (N, mean, SD, median, minimum, and maximum). From start/stop information, the proportion of exercise sessions completed and the proportion of patients which complete at least 50% of the exercise sessions along with associated 95% confidence intervals will be estimated. Additionally, descriptive statistics will be provided for the patient satisfaction survey provided at the end of the study.

To address Aim 2, we will use paired t-tests to examine change from baseline (T1) to 14 weeks (T2). For outcomes which are known to be non-normal such as biomarkers, we will use Wilcoxon-signed rank tests. We plan an intent-to-treat analysis. Even if we do not see significant differences, descriptive statistics including means, SD, and effect sizes (differences in means between the two time points divided by pooled SD) will be reported for outcomes along with 95% confidence intervals. All analysis will include checking of assumptions. Additionally, we will also use repeated measures ANOVA to estimate the contrast of interest (change from baseline at 14 weeks) for primary and secondary outcomes, after adjusting for age and baseline activity level.

For activity outcomes obtained from the FitBit, such as patients' daily number of steps, distance, active minutes, and heart rate, we will start with simple techniques such as paired t-tests or Wilcoxon signed-rank tests to compare the mean change in activity level from baseline (T1: summarized over week 6) to treatment end (T2: summarized over week 13). As an exploratory analysis, we will also use a generalized linear mixed model with appropriate distribution (e.g. Poisson) and link function fit to all weekly outcomes to examine changes over time using time as a continuous variable. We expect to have an abundance of information provided from the Fitbit, thus we will estimate descriptive statistics (N, mean, SD, median, minimum, and maximum) for all outcomes (i.e., number of steps, distance, active minutes, and heart rate) at each week to aid in planning future studies.

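### Section J.2 counts completed sessions from Fitbit button presses alone, so unrecorded sessions can distort the share of patients reaching 50%, and no cross-check against the Daily Log is planned

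*Combined protocol and SAP*

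**What the plan says.** Section J.2 opens Aim 1 with two measures: "adherence in the intervention group will be measured through a 5 question survey at each treatment and also through start/stop on the Fitbit". It then takes both summary proportions from one of them: "From start/stop information, the proportion of exercise sessions completed", and with it the share of patients who reach half or more of their sessions. The second proportion answers Aim 1, Hypothesis 1.

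Section I.4 (Adherence) is broader: "Adherence will be measured by self-report of session completion (See Appendix III) and activity tracking via FitBit". The outcome table in I.4 lists feasibility under Primary Outcome with two sources: "Percentage of subjects that can complete the 8-week intervention FitBit data Daily Log".

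The press is a manual act: "The patients will also be asked to hit a start EX button on the FitBit", and patients press again when they finish. Sections I.4 and I.7 say that the video reminds them to do both. The tracker also records heart rate continuously while worn, and I.4 (Physiological Parameters) states that "detectable elevations in heart rate are expected during EX sessions".

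No section says how to count a session that is logged but not pressed, started but not stopped, or done without a working tracker. J.3 deals with dropout only.

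**The concern.** Read as written, J.2 counts only sessions that left a start/stop record. Each patient, from age 5 upward, must press twice at each of 48 planned sessions on a device with a five-day battery. Some completed sessions will probably leave no record.

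The 50% cut magnifies the loss. A patient a little above the cut needs only a few missed presses to be classed as not reaching it, so a modest capture loss can move many patients across. The result is the main feasibility finding of a study meant to prepare a fully powered trial. A press-only count cannot separate patients who did not exercise from patients who did not press, and those two problems call for different remedies. The planned 95% confidence interval covers sampling error around the recorded share, not the gap between recorded and true completion.

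**Working it through.** **Plan's own figure.** H.1 gives power for paired t-tests but no sample size or precision for the adherence proportions, so there is nothing to reproduce on this point.

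**Inputs from the documents.** Home sessions are requested 6 times a week for 8 weeks (I.3): 6 × 8 = 48. The cut is 50% (section B): 24 sessions. Enrolment is 40 (section H).

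**Assumed inputs, none given in the documents.** Capture rate c, the chance that a completed session leaves a press record: 80% to 95%. Mean true completion μ: 60% to 90%, with 50% as an extra case. Between-patient intraclass correlation (ICC): 0.2, varied from 0.1 to 0.4.

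**Step 1: break-even.** Expected recorded sessions are c × true sessions. To expect 24 recorded, a patient must complete 24/c.
- c = 95%: 24/0.95 = 25.3 sessions (52.6%)
- c = 90%: 24/0.90 = 26.7 sessions (55.6%)
- c = 80%: 24/0.80 = 30 sessions (62.5%)

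**Step 2: one patient.** Recorded sessions follow Binomial(true sessions, c). A patient who truly completes 30 of 48 (62.5%) is recorded at 24 or more with probability 97% at c = 90% and 61% at c = 80%. A patient at exactly 24 is recorded at 24 with probability 0.95^24 = 29% at c = 95% and 0.90^24 = 8% at c = 90%.

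**Step 3: the cohort.** True sessions are beta-binomial with 48 trials, mean μ and Beta parameters μk and (1 − μ)k, where k = 1/ICC − 1. At ICC 0.2, k = 4, so μ = 60% gives Beta(2.4, 1.6). Recorded sessions are thinned as in step 2. Percentage of patients recorded at 24 or more (ICC 0.2):

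| Mean true completion | All captured | c = 95% | c = 90% | c = 85% | c = 80% |
|---|---|---|---|---|---|
| 60% | 68.1 | 64.6 | 60.5 | 55.9 | 50.5 |
| 70% | 82.0 | 79.4 | 76.2 | 72.4 | 67.6 |
| 80% | 91.9 | 90.4 | 88.5 | 86.0 | 82.8 |
| 90% | 97.6 | 97.1 | 96.3 | 95.3 | 93.9 |

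At 90% capture the loss is 68.1 − 60.5 = 7.6 points at mean 60%, 91.9 − 88.5 = 3.4 at mean 80%, and 97.6 − 96.3 = 1.3 at mean 90%. At mean 60% and 80% capture it is 68.1 − 50.5 = 17.6. Mean session completion is c × μ, so 60% becomes 0.9 × 60% = 54% or 0.8 × 60% = 48%.

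**Step 4: sensitivity to the ICC.** At mean 60% and 90% capture, the loss is 73.9 − 63.2 = 10.7 points at ICC 0.1 and 63.3 − 58.9 = 4.4 at ICC 0.4. Over means of 50% to 70% and ICCs of 0.1 to 0.4, it is about 4 to 12 points at 90% capture and 9 to 25 at 80%.

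**Step 5: error in the other direction.** Suppose 10% of sessions not completed are nevertheless recorded (assumed). At mean 60%, ICC 0.2 and 90% capture, the recorded share is 68.1%, equal to the true share. The upward error cancels the loss.

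**Step 6: scale.** The exact 95% interval for 24 of 40 runs from 43% to 75%, a half-width of about 16 points. A loss of 8 points is about half of that, and a loss of 18 exceeds it.

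**The case against.** The plan foresaw forgotten presses and built a reminder into the session videos. That stands, and it is a reason to favour the higher capture rates. A reminder does not charge the tracker or put it on, and the analysis has no fallback where it fails.

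Preferring a device record to self-report is a legitimate choice, because logs can over-report. This also stands. The point is that the sources are not reconciled, not that the press is a poor primary source.

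A reader might infer that self-report is ignored altogether. The documents do not support that: J.2 names the session survey as an adherence measure and summarises adherence scores. The gap concerns the two proportions.

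A reader might also infer that the plan expressly scores an unpressed session as not done, and that the error runs one way only. J.2 names the data source and is silent on the unpressed session; its loss follows from applying J.2 as written. Presses without a full session would err upward, and step 5 shows that they can offset the loss.

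Finally, the size is assumed throughout and is small when completion is high. The documents also attach no go/no-go rule to the share reaching 50%. Both are correct and limit the weight of the point.

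**Conclusion.** The concern holds in limited form. J.2 bases both Aim 1 proportions on presses alone, while I.4 gives the Daily Log and self-report as further sources, and no rule links them. Completed sessions without a press are lost, and the planned interval will not show it. The bias from missed presses is downward; the net bias is probably downward, but the documents do not establish that.

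The size rests on assumed capture, completion and ICC. At ICC 0.2, 90% capture costs about 1 to 8 points over mean completion of 90% down to 60%, and 80% capture at mean 60% costs about 18. A lower ICC or a mean nearer 50% makes the loss larger; a higher ICC or some false recordings make it smaller. The study's own data can show how far the sources disagree, so the change is worth making before analysis.

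**What to change.** In J.2, state before the data are examined that a session counts as completed if it has a start/stop record, or a Daily Log entry with a Fitbit heart-rate rise inside a pre-set window around the logged time of day. Set the size of that rise, and say how a start without a stop is treated. A rise at any time on the same day is too weak, since ordinary activity could confirm a mistaken entry.

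Report both proportions three ways: press only, log only and the combined rule. Present them as sensitivity analyses, not as bounds: a pressed but unlogged session is missing from the log-only count, and a false press can put the press-only count above true completion. Add the agreement between sources and the number of tracker non-wear days. An unworn or uncharged tracker leaves no heart-rate trace, so the combined rule cannot recover those sessions and only the log-only result can show them. Bring the adherence text and outcome table in I.4 into line with J.2.

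The cost is some extra analysis of data already collected. The log may over-report, which comparison with the press-only result makes visible.
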